### 10.ADVERSE EVENT REPORTING

## 10.1. Definitions

Table 2: Adverse event reporting definitions

Severity Definitions	Mild	Awareness of signs or symptoms that do not interfere with the participant's usual activity or are transient and resolved without treatment and with no sequelae.
	Moderate	A sign or symptom, which interferes with the participant's usual activity.
	Severe	Incapacity with inability to do work or perform usual activities.
Adverse Event	AE	Any untoward medical occurrence in a participant participating in the trial which does not necessarily have a causal relationship with the intervention received.
Related Event	RE	An event which resulted from the administration of any of the research procedures.
Serious Adverse Event	SAE	An untoward occurrence that:
		Results in death
		Is life-threatening*
		Requires hospitalisation or prolongation of existing hospitalisation
		Results in persistent or significant disability or incapacity
		Consists of a congenital anomaly/ birth defect
		Or is otherwise considered medically significant by the Investigator**
Unexpected Event	UE	The type of event that is not listed in the protocol as an expected occurrence.
Related and Unexpected Serious Adverse Event	-	A SAE that meets both the definition of a Related and Unexpected Event.

\* The term life-threatening is defined as diseases or conditions where the likelihood of death is high unless the course of the disease is interrupted.

## 10.2. Adverse event recording - general

The recording and reporting of Adverse Events (AEs) will be in accordance with the UK Policy Framework for Health and Social Care Research, the Principles of Good Clinical Practice (GCP) as set out in the UK Statutory Instrument (2004/1031; and subsequent amendments) and the requirements

\*\* Medical events that may not be immediately life-threatening or result in death or hospitalisation but may jeopardise the participant or may require intervention to prevent one of the other outcomes listed in the definitions above.

of the Health Research Authority (HRA). Definitions for adverse event reporting are listed in Table 2: Adverse event reporting definitions in Section 10.1.

It is routine practice to record AEs in the participant's medical notes and it is also recommended that this includes the documentation of the assessment of severity and seriousness and also of causality (relatedness) in relation to the intervention(s) in accordance with the protocol.

## 10.3. Adverse event reporting in UNiTY

The reporting period for AEs in UNiTY will be from the day the trial intervention starts until 60 days after the cycle outcome is known. For an unsuccessful cycle (i.e. biochemical pregnancy was not detected) SAEs should be reported for 60 days following the negative pregnancy test. For cycles resulting in pregnancy, SAEs should be reported for 60 days after the pregnancy outcome is known (i.e. live birth, still birth, termination or miscarriage). SAEs should only be reported for trial related treatments, with the exception of the first IVF cycle in the IUI arm. Any non-trial treatment related SAEs should be recorded in the medical notes but not reported to the trial office.

The safety profile for the trial population and interventions are well established, so although it is recommended that the severity, seriousness, and causality of all AEs for both participants and offspring should be recorded in the relevant medical notes, a strategy of targeted reporting of AEs will not affect the safety of participants. Related AEs will be captured as complications within the primary and secondary outcome measures. Only serious, related, and unexpected adverse events, beyond the routine expectations and known risks for fertility treatment, will be reported as SAEs.

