# **Arms**

Intervention: Three cycles of letrozole stimulated Intra Uterine Insemination (IUI).

Control: One cycle of In-Vitro Fertilisation (IVF) with standard ovarian stimulation and first fresh or frozen embryo transfer.

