## 10.4.3. Serious Adverse Events requiring expedited reporting to the Trial Office

All serious and related AEs must be reported to the Trial Office on a trial specific SAE form within 24 hours of the site research team becoming aware of the event.

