### 14.2.2. Secondary outcomes

The secondary outcomes that are binary (i.e., yes/no) will be analysed using the same methods as described for the primary outcome (see Section 14.2.1), with corresponding 95% confidence intervals (this includes the longer-term assessment at 25 months). For those secondary outcomes that are continuous (e.g. Gestational age at delivery, Birthweight, CSQ-8 score), mixed effects linear regression methods will be utilised to calculate an adjusted mean difference and 95% confidence interval. Time-to-event outcomes (e.g. TTP leading to a live birth) will be analysed using a mixed effects ('frailty') Cox Proportional Hazard model, allowing the same minimisation variables as fixed effects and randomising centre as a random effect. The treatment effect will be expressed as adjusted hazard ratio with 95% confidence interval. Regarding safety, the total number of participants experiencing SAEs will be given by allocation group along with a descriptive table of the events, and statistical significance will be determined by a chi-square test; other safety data including complications will be tabulated by group but are not expected to be formally analysed.

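### SAE reporting criteria conflict, and SAEs from non-trial follow-on treatment count in the IUI arm only, yet the arms are compared by a chi-square test

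*Protocol*

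**What the plan says.** **Which treatments are covered.** Section 10.3 limits SAE reporting by treatment: "SAEs should only be reported for trial related treatments, with the exception of the first IVF cycle in the IUI arm". It continues: "Any non-trial treatment related SAEs should be recorded in the medical notes but not reported to the trial office". After an unsuccessful cycle, "SAEs should be reported for 60 days following the negative pregnancy test"; after a conception, reporting runs to 60 days beyond the pregnancy outcome. Trial treatment is three letrozole-stimulated IUI cycles in one arm and "One cycle of In-Vitro Fertilisation (IVF) with standard ovarian stimulation and first fresh or frozen embryo transfer" in the other (Trial Summary, Arms). IVF after IUI is described as outside the trial intervention (Justification for choice of intervention; Section 7.1.1), and so are later frozen transfers in the IVF arm (Section 7.1.2).

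**Which events are covered.** Section 10.3: "Only serious, related, and unexpected adverse events, beyond the routine expectations and known risks for fertility treatment, will be reported as SAEs". Section 10.4.3: "All serious and related AEs must be reported to the Trial Office on a trial specific SAE form within 24 hours". Section 10.4.1 first sends serious and related events to the Trial Office, then says that events meeting the definition of serious need no SAE form. Section 10.4.2 has hospital admissions for OHSS, an expected event, reported within four weeks.

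**How SAEs are compared.** Section 14.2.2 counts participants with SAEs by allocation group, and "statistical significance will be determined by a chi-square test". It gives no common window and no rule attributing an event to a treatment cycle. The DMC also reviews SAEs (Section 10.6).

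**The concern.** There are two separate problems, and both feed the same count.

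First, a site cannot tell from Section 10 which serious events to report. A serious, related and expected event is left out by one section and required within 24 hours by another. If sites resolve this differently, the SAE table, the DMC's data and the onward reporting of unexpected related events to the ethics committee rest on mixed criteria.

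Second, non-trial follow-on treatment is observed in one arm only. Section 1.1.4 expects every couple unsuccessful after three IUI cycles to go on to IVF, so this cycle will be common in the IUI arm, and its SAEs are reported. A second IVF cycle or a further frozen transfer in the IVF arm is also non-trial, and its SAEs are not. Under Table 9, a conception from such further intervention within 270 days counts towards the IVF arm's primary outcome, so the benefit is counted while related SAEs are not collected.

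Lower risk is one of the stated attractions of IUI (Section 1.1.4). A between-arm SAE test should therefore have a clear meaning, either for the randomised courses or for the whole policies. As written it has neither.

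**Working it through.** **Part 1: the reporting criteria side by side**

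| Event | 10.3 | 10.4.1 | 10.4.2 | 10.4.3 |
|---|---|---|---|---|
| Serious, related, unexpected | report | report (first paragraph); no SAE form (second paragraph, taken literally) | not covered | within 24 hours |
| Serious, related, expected: OHSS admission | not an SAE report | same conflict | report within four weeks | within 24 hours, no exception stated |
| Serious, related, known risk, not listed as expected | depends on the definition of expectedness | same conflict | not listed | within 24 hours |

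The third row arises because expectedness has two definitions. Sections 10.1 and 10.5.2 call an event unexpected if the protocol does not list or define it as expected. Table 4 (printed in Section 10.5.3) calls it unexpected if it is inconsistent with known information about the procedures. Section 10.5.2 also has the chief investigator assess all related SAEs for expectedness. That presupposes that expected ones have been reported, contrary to Section 10.3.

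The three-way triage in Section 10.4 makes expedited reporting the residual category. This can settle 10.4.2 against 10.4.3, but not 10.3 against 10.4.3.

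**Part 2: size of the follow-on component**

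Inputs from Section 14.1: IUI success per cycle p = 6.4% (about 18% over three cycles) or 10.36% (28%).

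- IUI cycles per couple: c = 1 + (1 − p) + (1 − p)²
- Share going on to IVF, with full uptake as Section 1.1.4 expects: f = (1 − p)³

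At p = 0.064: c = 1 + 0.936 + 0.876 = 2.812, which reproduces the 281.2 cycles per 100 couples in Table 7; f = 0.820. (The couples-per-cycle row printed in Table 7 sums to 270.0 and belongs to the other scenario; the total is the figure that matches 6.4%.)

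At p = 0.1036: c = 1 + 0.8964 + 0.8035 = 2.700, which reproduces the 270 in Table 8; f = 0.720.

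So per 100 IUI-arm couples there are 270-281 reportable IUI cycles, which belong to the policy, plus 72-82 reportable follow-on IVF cycles, which are non-trial. In the IVF arm there is at most one reportable cycle per couple, and no follow-on treatment is reported.

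**Illustration.** The documents give no SAE rates. Assume 1.0% per IVF cycle and 0.1% or 0.2% per IUI cycle, with risks added across cycles.

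| Scenario | IUI risk per cycle | First-line IUI (c × risk) | Planned count, IUI arm (adding f × 1.0%) | IVF arm |
|---|---|---|---|---|
| 18% | 0.1% | 0.28% | 0.28 + 0.82 = 1.10% | 1.0% |
| 18% | 0.2% | 0.56% | 0.56 + 0.82 = 1.38% | 1.0% |
| 28% | 0.1% | 0.27% | 0.27 + 0.72 = 0.99% | 1.0% |
| 28% | 0.2% | 0.54% | 0.54 + 0.72 = 1.26% | 1.0% |

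With 471 couples per arm, 1.0% is 4.7 couples, 0.99-1.38% is 4.7-6.5, and the first-line 0.27-0.56% is 1.3-2.6.

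**Sensitivity.** Take IVF risks s of 1-3% per cycle, an IUI risk r per cycle, both scenarios, and P(any SAE, IUI arm) = 1 − (1 − r)^c × (1 − f·s). The IUI:IVF ratio of participants with an SAE is:

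| IUI risk per cycle | Follow-on IVF counted | Follow-on IVF not counted |
|---|---|---|
| None | 0.72-0.82 | 0 |
| One quarter of IVF | 1.38-1.52 | 0.67-0.70 |
| Equal to IVF | 3.29-3.58 | 2.63-2.79 |

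Counting the follow-on cycle always raises the ratio. Whether it crosses 1 depends on the assumed risks.

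**The case against.** **The design compares policies.** Analysis is by intention to treat, and IVF after failed IUI is part of what an IUI-first policy leads to. The complications outcome in Section 8.2.2.1 has a similar scope: the first IVF treatment within 450 days and the first three IUI cycles. On this view Section 10.3 deliberately covers each arm's first IVF cycle. This stands in part. A reader might infer that up to four reportable cycles against one is itself the fault, but the documents do not support that, because three IUI cycles against one IVF cycle is the comparison the trial was set up to make. What remains is that a policy-level comparison needs follow-on treatment in both arms, and here only one arm has it. The part left out may be modest: Section 1.1.1 says that a single funded attempt is most usual in England, though Scotland funds three and Wales two, and frozen transfers from the first cycle come on top. The protocol gives no figure for it.

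**The exception could mean the opposite.** It might be read as leaving out the follow-on IVF cycle. Since that cycle is already non-trial, such an exception would be redundant. If it was meant, the follow-on asymmetry disappears, but the sentence still needs correcting.

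**The consequence is limited.** Section 14.2 calls all secondary outcomes exploratory, the SAE test comes with a descriptive table, and complications are collected separately and not tested. That is fair, and it lowers the stakes. It does not settle which events enter the SAE count.

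**Section 10.4.1 may be loosely worded.** Its second paragraph was probably meant only for events that are not related. That is plausible, but the text does not say so.

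**Conclusion.** Both parts hold in limited form. The conflict among Sections 10.3 and 10.4.1 to 10.4.3, and between the two definitions of expectedness, is plain on the text and needs no assumption. The follow-on asymmetry holds on the natural reading of Section 10.3 and concerns only non-trial treatment: 72-82 first IVF cycles per 100 couples are counted in the IUI arm, against no follow-on treatment in the IVF arm. By the notes to the schedule of assessments these cycles start no earlier than 270 days.

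The numerical effect is illustrative. Under the assumed 1.0% and 0.1-0.2% risks, a first-line contrast of about 0.3-0.6% against 1.0% becomes about 1.0-1.4% against 1.0%. The real first-line difference is hidden and might be reversed. This rests on those risks, full uptake of IVF after failed IUI, and independence between cycles.

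Two stronger conclusions might be inferred and are not supported. One is that the direction will reverse: at the low end of the 28% scenario the result is 0.99% against 1.0%, and with no IUI risk the ratio stays below 1. The other is that, say, an admission for pelvic infection after egg collection would be lost. It is reportable under Section 10.4.3, and under Section 10.3 as well if unexpected means not listed in the protocol. Pelvic infection and ward admission are in any case collected as complications.

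**What to change.** 1. Reconcile Sections 10.3, 10.4.1, 10.4.2 and 10.4.3 so that they state one criterion for which SAEs go to the Trial Office, on which form and by when. Use one definition of expectedness in Sections 10.1, 10.5.2 and Table 4. Which criterion to adopt is for the sponsor.
2. Reword the exception in Section 10.3 so that it says directly whether SAEs from the follow-on first IVF cycle in the IUI arm are reported.
3. In Section 14.2.2, base the between-arm SAE comparison on events from the randomised course: up to three IUI cycles against one IVF cycle with its first transfer. Tabulate SAEs from the follow-on IVF cycle separately, without pooling.
4. If a policy-level comparison is wanted, apply the same follow-on coverage in both arms.

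Items 1 to 3 are changes of wording. The restricted comparison needs no new data, provided that the SAE form shows which treatment cycle an event belongs to. Item 4 would require SAE reporting for further IVF cycles and transfers in the IVF arm. It should be decided early, because an analysis plan cannot recover events that were never reported.

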# Risk

The main risk associated with IVF is ovarian hyperstimulation syndrome (OHSS), which causes ovaries to become enlarged and fluid to leak into the abdomen. When mild this is uncomfortable and interferes with daily activities. However, when severe, patients are at high risk of blood clots and may need to be hospitalised. IVF also involves egg collection, a surgical procedure with the most common risks being bleeding and pelvic infection.

Multiple pregnancy with twins is highly risky for the pregnant partner and the babies, with the HFEA acting via regulation to minimise these occurrences. There are some concerns that the rates of multiple pregnancies may be higher in IUI compared to IVF (single embryo transfer is well-controlled by regulation). However, there is also evidence to say that the numbers are comparable (5).

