## **Complications**

The following outcomes will be assessed:

i.) for the first IVF treatment within 450 days post randomisation for a period of 60 days following the date of FSH injection;

- ii.) for the first three IUI cycles within 450 days post randomisation for a period of 30 days following the date of ovarian stimulation for partial or cancelled cycles, or date of insemination for complete cycles.
  - Ovarian hyperstimulation syndrome (mild, moderate, severe);
  - Pelvic infection;
  - Bleeding post oocyte retrieval (IVF only);
  - o Admission to High Dependency Unit (HDU)/ Intensive Therapy Unit (ITU), standard ward admission, A&E visit or Outpatient review.

The following outcomes will be assessed at 28 days post birth (or patient's discharge date from hospital whichever is sooner).

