#### Antenatal

- Placenta praevia;
- Antepartum haemorrhage;
- Pregnancy-induced hypertension;
- PET/Pre-eclampsia/HELLP;
- Obstetric cholestasis;
- o Preterm pre-labour rupture of membranes;
- Gestational diabetes;
- Other significant complication

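### Protocol section 10.3 says related adverse events are captured as complications, but the treatment-phase list is closed at four items, and sections 10.3 and 10.4 disagree on which serious related events are reported

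*Protocol*

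**What the plan says.** Section 10.3 states that "a strategy of targeted reporting of AEs will not affect the safety of participants", citing the established safety profile, and supports this with two sentences. The first is "Related AEs will be captured as complications within the primary and secondary outcome measures". The second is "Only serious, related, and unexpected adverse events, beyond the routine expectations and known risks for fertility treatment, will be reported as SAEs".

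Section 8.2.2.1, under Complications, defines what is assessed after treatment:

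- OHSS, graded by severity
- "Pelvic infection"
- "Bleeding post oocyte retrieval (IVF only")
- health-care contact by level: HDU or ITU, ward, A&E or outpatient review

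The antenatal list in the same section ends with "Other significant complication", and the neonatal list ends with the same entry. The treatment-phase list has no such entry.

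On the danger of OHSS, section 1.1.2 says that "when severe, patients are at high risk of blood clots and may need to be hospitalised".

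Section 10.4.1 sends serious, related events to the trial office. Section 10.4.3 requires every adverse event that is both serious and related to go on the trial's SAE form within 24 hours. Neither adds a condition that the event be unexpected. Section 10.4.2 names OHSS admissions as the one pre-defined expected SAE, reported on CRFs without urgency. Section 14.2.2 plans SAE participant counts by arm, a chi-square test and a descriptive table of events. Complications are tabulated by arm without formal analysis.

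**The concern.** The section 10.3 sentence is unqualified and carries weight, because it is the reason offered for collecting adverse events selectively. If the outcome lists do not hold the related events, the reason fails for those events.

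Secondary clinical objective 3 in section 2.2.1 is to compare complication rates between the arms, and section 1.1.4 presents IUI as the lower-risk option. A comparison of treatment complications can show only the harms for which there is a line.

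For serious events the matter is one of consistency. If two sections of the protocol set different thresholds, two sites can handle the same event differently. The SAE counts seen by the DMC (section 10.6), and the arm comparison tested in section 14.2.2, would then depend partly on which section each site followed.

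**Working it through.** No sample size, power or error rate bears on this point, so the check is a count of list items and a trace of each route by which a treatment-related event could reach a by-arm table.

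**Count of items (section 8.2.2.1)**

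- Treatment-phase list: 4 items. Three are diagnoses, one of them restricted to IVF. The fourth records where care was given, not what happened.
- Open entries: 0 in the treatment-phase list, 1 in the antenatal list, 1 in the neonatal list. The short intrapartum and post-partum lists have none either, but they do not concern the treatments being compared.
- Mentions of clot, thrombosis or thromboembolism in any outcome list: 0.
- The primary outcome (section 8.2.1) is live birth at 34 weeks or later and holds no complication, so only the secondary outcomes can do what section 10.3 claims.

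**Routes for a treatment-related event outside the three named diagnoses**

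| Event | Governing text | Tabulated by type? |
|---|---|---|
| Non-serious | 8.2.2.1 | No line; at most an A&E visit or outpatient review |
| Serious, under 10.4.1 and 10.4.3 | SAE form, then 14.2.2 | Yes, in the descriptive SAE table |
| Serious and a known risk, under 10.3 as worded | Not reported as an SAE | Not as an SAE; appears as an admission and, where relevant, an OHSS grade |
| Arising during pregnancy | Antenatal open entry | Possibly |

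The first row holds whichever SAE rule is followed. The second and third rows can apply to the same event and give different results.

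The last row is a limited substitute. The antenatal items are assessed at 28 days after birth, or at discharge if sooner, so they do not serve couples without a birth. On the section 14.1 planning rates of 28% (IVF) and 18% (IUI at the margin), 100 − 28 = 72% and 100 − 18 = 82% of couples would have no primary-outcome birth.

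**The conflict over serious events**

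Section 10.3 sets three conditions (serious, related, unexpected) and adds that the event lie beyond the known risks of fertility treatment. Sections 10.4.1 and 10.4.3 set two (serious, related). The definition of unexpected does not settle it. The definitions table in section 10.1, and section 10.5.2, treat as unexpected anything the protocol does not list as expected, and section 10.4.2 lists only OHSS admissions. The expectedness table in section 10.5.3 instead asks whether the event is consistent with known information about the procedures. A clot after severe OHSS is unexpected on the first test, because it is not listed. It is arguably expected on the second, because section 1.1.2 describes it.

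**The case against.** The strongest reply is that serious events already have a route. A clot that leads to admission, threatens life or is judged medically significant meets the SAE definition. If judged related, it goes on an SAE form under 10.4.3 and appears by type in the section 14.2.2 table. Even SAEs exempt from reporting are to be recorded on CRFs (section 10.4.1). This stands, with the limit that section 10.3 as worded would stop such an event at the known-risk condition. A reader might infer that blood clots and similar events are never counted by type in either arm. The documents do not support that.

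A second reply is that section 11.2 times the Post-Treatment CRF so as to catch all possible complications, and its fields are not shown. An open field may already exist. This also stands: the omission is shown for the pre-specified outcome list, not for the form.

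A third concerns direction. A reader might infer that a list with one IVF-only item and nothing specific to letrozole or insemination makes IUI look safer. The documents do not support this. The one missing event that they name, blood clots, is described as a consequence of severe OHSS, which they call the main risk of IVF; missing it would flatter IVF. They name no unlisted harm specific to IUI. The IUI safety concern that they do raise, multiple pregnancy, is a secondary outcome, as are ectopic pregnancy and cycle cancellation for over-response.

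Finally, secondary outcomes are exploratory and complications are only tabulated. That limits the consequence, but it does not make the section 10.3 sentence correct.

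**Conclusion.** The point holds in a limited form. The assurance in section 10.3 is broader than the outcomes can deliver: the treatment-phase list is closed at four items, so related non-serious events outside the named diagnoses are not tabulated by type under any reading of the SAE rules. Whether serious, related, known-risk events reach the SAE table and its chi-square test depends on a contradiction between section 10.3 and sections 10.4.1 and 10.4.3 that the protocol leaves open.

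No count of affected couples can be given, because the documents contain no rates for such events; any figure would rest entirely on an assumed rate. No direction of bias between the arms is shown. The conclusion about the list rests on section 8.2.2.1 as written and on the CRF fields being unseen. If the form already has an open item, the remaining defects are the outcome list, the wording of section 10.3 and the SAE conflict. The change is worth making because it is cheap and serves secondary objective 3. It does not affect the primary analysis.

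**What to change.** 1. Add to the treatment-phase complication list in section 8.2.2.1, for both arms, an item such as *Other significant treatment-related complication (specify)*, with thromboembolism as a named option. Add the same item to the Post-Treatment CRF if it is not already there.
2. Reword section 10.3 to say that related adverse events are captured in the secondary complication outcomes, including this item, and remove the reference to the primary outcome.
3. Reconcile section 10.3 with sections 10.4.1 and 10.4.3, and align the two definitions of expectedness (sections 10.1 and 10.5.2 against the expectedness table), so that every site applies one SAE reporting rule. Which rule to adopt is for the sponsor to decide.

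The cost is at most one extra CRF item with a free-text field, a little data entry and coding, and a few sentences of protocol text. No treatment, visit or primary analysis changes.

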## 10.4. Serious Adverse Advents (SAE) reporting in UNiTY

For all SAEs, the PI or delegate must do one of the following:

- Record safety reporting-exempt SAEs in the medical notes but not report them to the trials office on an SAE form as per Section 10.4.1 Serious Adverse Events not requiring reporting to the Trial Office.
- 2. **Report SAEs to the trial office in a non-expedited manner**. This can only be done for the predefined subset of SAEs as per Section 10.4.2 Serious Adverse Events requiring non-expedited reporting to the Trial Office.
- 3. **Report SAEs to the trial office in an expedited manner** (within 24 hours of the site research team becoming aware of the event). All SAEs not covered by the above 2 categories must be reported as per Section 10.5 SAE Reporting process.

**Note**: when an SAE occurs at the same hospital at which the participant is receiving trial intervention or is being followed up for trial purposes, processes must be in place to make the trial team at the hospital aware of any SAEs, regardless of which department first becomes aware of the event, in an expedited manner.

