### 10.4.1. Serious Adverse Events not requiring reporting to the Trial Office

At whatever time they occur during an individual's participation, from commencement of intervention up to 60 days after the cycle outcome is known, only serious and related SAEs will be reported to the trial office. SAEs that do not fall into these categories will be recorded on follow up CRFs.

All events which meet the definition of serious must be recorded in the participant notes, including the causality and severity, throughout the participant's time on trial, including follow-up, but for trial purposes these events do not require reporting on the SAE Form. Such events are "safety reporting exempt". They will be recorded on the treatment CRFs as part of trial follow-up.

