## 10.4.2. Serious Adverse Events requiring non-expedited reporting to the Trial Office

As the safety profile of the interventions are well established, the causal relationship between the intervention (or the participant's underlying condition), and the SAE, may be known. That is, such events are protocol-defined as "expected" (see Section 10.5.2 Assessment of expectedness of an SAE by the CInvestigator (CI)).

Such events should still be recorded by the trial team in the participant's notes and reported to the Trial Office on the relevant CRFs, but do not require expedited reporting (i.e. immediately on the site becoming aware of the event) since the assessment of expectedness for the specified events has been pre-defined. This includes:

Hospital admissions due to OHSS

This information should be uploaded onto the trial database within four weeks of the event.

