## 10.5.3. Provision of SAE follow-up information

Following reporting of an SAE for a participant, the participant should be followed up until resolution or stabilisation of the event. Follow-up information should be added to the original SAE form. Once the SAE has been resolved, all critical follow-up information has been received and the paperwork is

**Table 4**: Categories of expectedness

Category	Definition
Expected	An adverse event that is consistent with known information about the trial related procedures.
Unexpected	An adverse event that is not consistent with known information about the trial related procedures.

complete, a copy of the final version of the completed SAE form must be submitted to the Trial Office and the original kept in the ISF.

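### Section 10 gives sites conflicting instructions on which serious events go on the SAE form and how quickly

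*Protocol*

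**What the plan says.** All of the following is current protocol text.

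- **Section 10.3** limits SAE reports by seriousness, relatedness and expectedness together: "Only serious, related, and unexpected adverse events, beyond the routine expectations and known risks for fertility treatment, will be reported as SAEs".
- **Section 10.4** sets three routes: exempt (10.4.1), a predefined non-expedited subset (10.4.2), and the remainder expedited. On the last it says: "All SAEs not covered by the above 2 categories must be reported".
- **Section 10.4.1, first paragraph**, sets no expectedness condition: "only serious and related SAEs will be reported to the trial office". SAEs outside that description go on follow-up CRFs.
- **Section 10.4.1, second paragraph**, takes as its subject every event that meets the definition of serious, and says that "for trial purposes these events do not require reporting on the SAE Form".
- **Section 10.4.2** covers SAEs treated as expected. They go on CRFs, to be uploaded within four weeks of the event. One item is listed: "Hospital admissions due to OHSS".
- **Section 10.4.3** has no exception for that item: "All serious and related AEs must be reported to the Trial Office on a trial specific SAE form within 24 hours".
- **Section 11.2, Table 6**, places non-expedited events on the SAE form itself, with four weeks counted from the site becoming aware. It describes SAE forms as emailed, whereas Section 10.5 has them completed on REDCap.
- **Expectedness.** Section 10.1 defines an unexpected event as "The type of event that is not listed in the protocol as an expected occurrence", and Section 10.5.2 repeats that test for the CI. Table 4, printed in Section 10.5.3, defines an expected event as "An adverse event that is consistent with known information about the trial related procedures". Section 10.5.2 refers the CI to Table 5 for the criteria, but Table 5 is the source-data table in Section 11.1.

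**The concern.** These are working instructions to site staff on safety reporting, so a later analysis plan cannot settle them. A site that follows Section 10.3, or the second paragraph of Section 10.4.1, to the letter would not send in related serious events that Section 10.4.3 wants within 24 hours. An event that is not sent in gets no independent causality review (Section 10.5.1), no expectedness assessment (Section 10.5.2), and no place in the feed to the 15-day report on related and unexpected SAEs (Section 10.6). Two sites acting in good faith could handle the same event differently.

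**Working it through.** No arithmetic applies. The check takes four classes of serious event and applies each instruction literally. OHSS admissions are taken as judged related.

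| Instruction | Related, not a known risk | Related, known risk other than OHSS admission | OHSS admission | Not related |
|---|---|---|---|---|
| 10.3 | SAE report | No SAE report, if the known-risk wording governs | No SAE report | No SAE report |
| 10.4.1, para 1 | To trial office | To trial office | To trial office | Follow-up CRFs |
| 10.4.1, para 2 | No SAE form | No SAE form | No SAE form | No SAE form |
| 10.4.2 | Not addressed | Not listed | CRFs, 4 weeks from event | Not addressed |
| 10.4.3 | SAE form, 24 h | SAE form, 24 h | SAE form, 24 h | Not addressed |
| 11.2, Table 6 | SAE form, 24 h if expedited | SAE form, 24 h if expedited | SAE form, 4 weeks from awareness if non-expedited | Not addressed |

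Reading down the columns gives four conflicts.

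1. **Known risks other than OHSS admission.** Section 1.1.2 names pelvic infection among the most common risks of egg collection. A related admission for pelvic infection is off the SAE route under the known-risk wording of 10.3 and on it within 24 hours under 10.4.3. Section 10.5.2 has the CI assess all related SAEs for expectedness, so it presupposes that expected ones arrive. Section 10.3 would have the site filter them out first.
2. **The exemption paragraph.** The second paragraph of 10.4.1 removes every class from the SAE form, including related and unexpected events. Section 10.4 defines its exempt route by pointing to 10.4.1, so on the literal reading the other two routes are left empty.
3. **OHSS admission.** Three combinations are written: CRFs within four weeks of the event, SAE form within four weeks of awareness, and SAE form within 24 hours. Form, clock length and clock start all vary.
4. **Expectedness.** For the pelvic-infection admission, the test in Sections 10.1 and 10.5.2 gives unexpected, since 10.4.2 lists only OHSS admissions. The Table 4 test gives expected, since the protocol itself calls it a common risk. Under the first the 15-day report in Section 10.6 is due; under the second it is not.

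**The case against.** The best defence is that Section 10.4 is the routing frame and the rest should be read under it. Section 10.4.3 is then the residual route, and OHSS admissions, being named in 10.4.2, are not 24-hour events. If unexpected means not listed in the protocol, and only OHSS admissions are listed, then serious, related and unexpected in 10.3 is the same set as the 10.4 residual. Section 10.5.2 repeats that test, which favours it over Table 4. The second paragraph of 10.4.1 follows a sentence about SAEs outside the reportable group, so it was probably meant for SAEs that are not related.

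Much of this stands. A reader might infer that the section contains four wholly incompatible rules. It does not: 10.4, the first paragraph of 10.4.1 and 10.4.3 agree if 10.4.3 is read as residual. But the harmonised reading has to be supplied by the site. Section 10.4.3 states no exception, the exemption paragraph states no limit, and the known-risk wording in 10.3 reaches further than the listed-event test. The frame also leaves the difference in form and clock start between 10.4.2 and Table 6 untouched.

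A reader might also infer that safety capture as a whole depends on which paragraph a site follows. The protocol does not support that. OHSS by severity, pelvic infection and admissions are secondary outcomes (Section 8.2.2.1), complications are collected on the Post Treatment CRF (Section 9.1), congenital anomalies have their own CRF entry (Section 10.8), and exempt SAEs still go in the notes and on CRFs (Section 10.4.1).

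**Conclusion.** The instructions conflict as written and need correcting. The firm conflicts are 10.3 against 10.4.1 (first paragraph) and 10.4.3 on known-risk events; the second paragraph of 10.4.1 against the rest; 10.4.2 against 10.4.3 and Table 6 for OHSS admissions; and the two definitions of expectedness. The emailed wording in Table 6 and the wrong table reference in 10.5.2 are minor slips in the same text.

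The effect is confined to SAE-form and 24-hour capture, CI review and ethics reporting. It is tempting to add that the between-arm chi-square test of participants with SAEs (Section 14.2.2) is compromised. That holds only if SAEs are counted from SAE forms, and Section 14.2.2 does not name the source. The protocol gives no rate of OHSS or pelvic-infection admission, so no count of couples moving in or out of the SAE total can be supported. The conclusion rests on the wording alone.

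**What to change.** Reconcile Sections 10.1, 10.3 to 10.4.3, 10.5.2, Table 4 and Table 6 into one routing table that follows the three routes of Section 10.4. The sponsor should choose the single rule and state it. Specifically:

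- limit the second paragraph of 10.4.1 to the SAEs that are not reportable under its first paragraph;
- add to 10.4.3 an exception for events listed in 10.4.2;
- align 10.3 with the chosen rule, so that the known-risk wording either goes or is tied to a named list;
- keep one definition of expectedness and correct the table reference in 10.5.2;
- state one form and one clock start for 10.4.2 events, and match Table 6 to it;
- replace the emailed wording in Table 6 with REDCap submission.

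The cost is a protocol wording change and a short notice to sites. No new data collection is needed.
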